Despite the important contribution of inflammation to depression, not all individuals exposed to increased inflammation develop depression.⁵ Less than 30% of patients treated with high doses of IFN- α develop major depressive episodes³; and even when endotoxin is experimentally administered inducing robust systemic inflammation, largely variable increases in depressive symptoms are found.⁴ Indeed, we have shown that depressive responses to endotoxin are far more accentuated in females.¹⁴ In line with our experimental data, the female preponderance in the prevalence of depression is a well-established finding, indicating a higher depression risk in females than males.^{6,7} Moreover, women show higher levels of inflammatory markers,²⁶ and there are well-known sex differences in the prevalence of inflammatory disorders, with females being between 2 and 9 times as likely as males to develop autoimmune disorders.²⁷

However, the female preponderance of depression prevalence decreases in the post-menopausal period,²⁸ and females show a nearly 3-fold decrease in depression incidence from ages 20 to 60. Rates of depression in males, by contrast, remain stable.²⁹ Likewise, levels of systemic inflammation are higher in females than in males, but this sex gap decreases with age.²⁶ Thus, it is unknown whether the vulnerability to inflammation-induced depression evident among younger women remains in later life. If this study shows older females to be more vulnerable to endotoxin-induced depression than older males, the finding will be significant as it would direct prioritization of female older adults for depression prevention. If this study shows no sex differences, the finding will also be significant as it would suggest age-related changes in sex differences and inform future studies on underlying inflammatory and affective mechanisms.

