
C.2.2. Overview of study design

To address Aim 1, examining sex differences in affective sensitivity to inflammation among older adults, we will select a total of 80 healthy older adults aged 60-80 years (40 males and 40 females), who are absent of current psychiatric illnesses, insomnia, and medical conditions (e.g., inflammatory disorders), into a placebo-controlled, randomized, double-blind, experimental inflammatory challenge protocol. Participants will be randomly assigned to receive either endotoxin (n=40) or placebo (n=40) in a between-subjects manner, stratified by sex. To address Aim 2, examining age differences in affective sensitivity to inflammation among females, we will recruit an additional 40 healthy premenopausal adult women (age 30-40) to be randomly assigned to receive endotoxin (n=20) or placebo (n=20).

For all participants, administration of endotoxin (0.8 ng/kg body weight vs. placebo), will be followed by self-report measures of depressed mood, negative and positive affect, and sickness symptoms (e.g., fatigue) assessed hourly over a 12-hour period; objective ratings of depressive symptoms by an observer blind to condition will be made every 2 hours. Behavioral tasks will be administered to coincide with peak onset of depressed mood, which we have previously shown to occur at 2 hours in both older and younger adults. Our prior protocol duration was 6 hours, but the current proposal will test for the presence of delayed termination of response^{57,58} and extend protocol duration to 12 hours. At baseline and starting two hours post-injection, at peak cytokine- and depressed mood responses, participants will complete the Probabilistic Reward Learning task⁵⁰⁻⁵², the Effort Expenditure for Reward Task,⁵⁹ the Social Choice task (i.e., intersection of reward

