Inclusion Criteria: Participants will be healthy older adults aged 60-80 years. For the younger sample, inclusion criteria will be healthy, biologically female adults between the ages of 30 and 40. By using this age range we will focus on women prior to the perimenopause or menopause transition who are also at high risk (median age of onset for mood disorders is 30; of note most studies using endotoxin have a mean age of participants well below age 30).^{66,67}

Exclusion Criteria: Participants will be excluded with a current medical or psychiatric disorder or who report current use of medications such as antidepressants and anti-inflammatory drugs, consistent with prior endotoxin protocols involving elderly subjects.^{41,58,68} For the younger sample, males will be excluded for the following reasons: feasibility, reduction of variability and subsequent enhanced power, and to build upon our prior observation of accentuated affective sensitivity to inflammation among women. Other exclusion criteria include pregnancy or planning to become pregnant; presence of chronic mental or physical illness, history of allergies, current and regular use of prescription medications, and nightshift work or time zone shifts (>3 hours) within the previous 6 weeks, or previous history of fainting during blood draws. See Protection of Human Subjects section for full details.

C.2.4. Experimental Procedures

Recruitment and Enrollment: Recruitment for the younger female sample will use existing infrastructure in place for the parent project, including identification of potential participants through the GENESYS Sampling System (Fort Washington, PA), which records telephone numbers and mailing addresses of households across the United States. This will allow us to select for households with at least one female person aged 30-40 years and living in the greater Los Angeles area; age information is based on known age-related data or a statistical estimate of age, predicted using individual household characteristics and Census demographic information.

Research staff are in place to send out recruitment letters and respond to inquiries by phone. Interested individuals will go through a two-step screening and assessment procedure to ensure that they are eligible for participation in the study. The initial screening process will be completed by phone; eligible and interested participants will then be scheduled for an in-person morning screening and assessment session (Visit 1).

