In our endotoxin study of younger adults, the effect of endotoxin on depressed mood was large in females ($d=0.70$) while minimal in males ($d=0.003$).¹⁴ Among older adults, we expect to see a smaller but still substantial difference of effect between sexes. In our endotoxin study of older females (K23AG049085, PI [name]), as shown in C.1.1.3, the effect size of endotoxin on depressed mood was still large but expectedly smaller ($d=0.51$) than in younger females. For Aim 1, based on these estimates, the assumed minimal effect size in older males ($d=0.003$), and the use of matching and multivariate regression analyses, with 40 older healthy females and 40 older healthy males, we expect a power $>80\%$ ($\alpha=.05$, two-tailed). For Aim 2, assessing differences between younger and older females, our previous work with several of the behavioral reward tasks has yielded moderate effect sizes when assessing the relationship between increases in IL-6 and task performance (e.g., $f^2 = 0.22, 0.32$). Given this range of effect sizes, a multiple regression analysis with three predictors of interest (age, group, age x group interaction) and two covariates (BMI, education level) would require a sample size of 38 to 75 to detect effects with 0.80 power. This work has relied on very mild increases in IL-6, and we expect endotoxin to yield stronger effects. Indeed, prior work with the endotoxin model has shown significant differences on a reward motivation task with a sample of 29 participants (15 saline placebo, 14 endotoxin),⁹² and greater feelings of social disconnection following endotoxin vs. placebo were observed in a small sample of women ($n=20$; age 18-36) in our previous study. Thus, the current study aims to recruit 40 premenopausal women with equal randomization between the endotoxin and saline group, and an additional 40 females will be drawn from the parent study for a total sample of 80.

C.3. Interpretation of Results and Potential Concerns

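### A non-significant sex difference in older adults would not show that the sex gap changes with age: the study has no young men, and its interval for the gap may be wide

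*Combined protocol and SAP*

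**What the plan says.** Section A.1 discusses both possible outcomes of Aim 1. Of the null one it says: "If this study shows no sex differences, the finding will also be significant as it would suggest age-related changes in sex differences". The sentence ends by saying that such a finding would inform later mechanistic work.

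Aim 1 uses 40 older women and 40 older men without insomnia (C.2.2, C.2.3). On allocation, C.2.2 says: "Participants will be randomly assigned to receive either endotoxin (n=40) or placebo (n=40) in a between-subjects manner, stratified by sex". That gives 20 per sex-by-condition cell. The younger sample is 40 women aged 30–40. C.2.3 says: "For the younger sample, males will be excluded for the following reasons: feasibility, reduction of variability and subsequent enhanced power".

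C.2.8 tests sex by condition in older adults (Aim 1) and age group by condition in women (Aim 2). It gives no confidence-interval or equivalence rule for concluding that there is no sex difference, and no comparison with younger men. C.3, on interpretation, does not address a null result either.

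C.2.9 says that in the group's study of younger adults "the effect of endotoxin on depressed mood was large in females" (d = 0.70) and minimal in males (d = 0.003). For older women, "the effect size of endotoxin on depressed mood was still large but expectedly smaller ($d=0.51$) than in younger females". Older men are assumed to be at 0.003. It concludes: "with 40 older healthy females and 40 older healthy males, we expect a power $>80\%$ ($\alpha=.05$, two-tailed").

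**The concern.** A non-significant interaction can arise because the gap is absent or because the study is too imprecise to see it. The sentence in A.1 takes the first explanation and then goes further, to a change with age. If the results are written up along those lines, an uninformative result could be published as evidence that women's greater affective sensitivity to inflammation fades in later life. That bears on the study's stated purpose of deciding whether older women should be prioritised for depression prevention.

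**Working it through.** **Is a change in the gap estimable?** Write each letter pair as an endotoxin-minus-placebo effect: YF, YM, OF, OM for young and old, female and male. The change in the sex gap with age is

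(YF − YM) − (OF − OM) = (YF − OF) − (YM − OM).

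Aim 1 estimates OF − OM and Aim 2 estimates YF − OF. Nothing in this study estimates YM, so the second bracket is missing. It cannot be taken as zero: A.2 allows that ageing may raise sensitivity to inflammation regardless of sex.

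**Inputs (C.2.2, C.2.3, C.2.9).** 20 per cell; two-sided alpha 0.05; young-adult gap 0.70 − 0.003 = 0.697 SD; planned older-adult gap 0.51 − 0.003 = 0.507 SD.

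**The plan's own figure.** C.2.9 states more than 80% power. For the interaction, SE = √(4/20) = 0.447 SD. At 0.507 the noncentrality is 0.507/0.447 = 1.134, which on 76 df gives power 0.201. The stated figure is not reproduced. A plain 40 versus 40 comparison at 0.507 gives only 0.61. Reaching 80% for the interaction with 20 per cell would need covariates explaining about 84% of the variance.

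**Base case: d on the SD of the analysed outcome, no gain in precision.**
- Gap 0.697: 0.697/0.447 = 1.559, power 0.337, so missed about 66% of the time.
- Gap 0.507: power 0.201, so missed about 80% of the time.
- 95% CI half-width: 1.992 × 0.447 = 0.89 SD. An estimate of exactly zero would still include 0.697.

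**Range.** The documents give no R² or correlation, so these values are assumptions. For covariates, SE = √(0.2 × (1 − R²)). For a baseline-adjusted mean of 12 hourly scores under compound symmetry with a constant effect, SE = √(0.2 × v), where v = (1 + 11r)/12 − r².

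| Assumption | SE | Power, 0.697 | Power, 0.507 | Half-width |
|---|---|---|---|---|
| None | 0.447 | 0.337 | 0.201 | 0.89 |
| R² = 0.25 | 0.387 | 0.427 | 0.253 | 0.77 |
| R² = 0.50 | 0.316 | 0.586 | 0.353 | 0.63 |
| 12-hour mean, r = 0.3 | 0.232 | 0.844 | 0.580 | 0.46 |
| 12-hour mean, r = 0.5 | 0.242 | 0.813 | 0.545 | 0.48 |
| 12-hour mean, r = 0.7 | 0.217 | 0.888 | 0.636 | 0.43 |
| 12-hour mean, r = 0.8 | 0.188 | 0.956 | 0.759 | 0.37 |

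The last four rows are optimistic, because C.1.1.3 reports that depressed mood peaks at 2 hours.

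**How firm is the young-adult benchmark?** C.1.1.1 describes 115 participants, 69 of them women, hence 46 men. Assuming equal arms within sex, SE = √(2/34.5 + 2/23) = 0.381, a half-width of about 0.75 SD. A comparison across the two cohorts has SE = √(0.447² + 0.381²) = 0.587. Its power to detect complete loss of a 0.697 gap is about 22% (0.697/0.587 = 1.19).

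**The case against.** The strongest reply is that nothing in the plan obliges anyone to draw this conclusion. A.1 is a rationale, its verb is tentative, and A.2 treats persistence of the sex gap into late life as an open question. This stands. A reader might infer that the plan pre-specifies a rule turning non-significance into a positive claim. It does not: C.2.8 and C.3 contain no such rule.

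The second reply is that the base case ignores the planned mixed models with hourly scores and what C.2.9 calls "the assumed minimal effect size in older males ($d=0.003$), and the use of matching and multivariate regression analyses". This also stands in part. A reader might infer that the study would miss the full young-adult gap two times in three. That holds only under the base-case assumptions, because the documents do not say how d was standardised. The same formula applied to the young cohort gives 0.697/0.381 = 1.83, p about 0.07, whereas C.1.1.1 reports that sex difference at P<0.05. The reported analysis may therefore have been more precise than the formula allows. The interval width carries the same condition: from R² = 0.50 upward in the table, an estimate of zero would exclude 0.697.

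Third, young men do exist in the earlier cohort, so an indirect comparison is possible. It is not planned in C.2.8. It would set a cohort of mean age 24.1 followed for 6 hours against a 12-hour protocol. It makes the inference weak rather than impossible.

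**Conclusion.** The point holds as a fault of interpretation. That the study cannot itself estimate a change in the sex gap with age follows from the design and needs no power assumption. That a null is weak evidence of no gap depends on precision. Power for the full young-adult gap is about 34% in the base case, 43–59% if covariates explain 25–50% of the variance, and 81–96% under the optimistic 12-hour average. For the gap that the plan itself expects in older adults, the base case is about 20% and even the optimistic range is only about 55–76%. Missing that smaller gap is therefore a real possibility throughout. These figures concern depressed mood, the outcome for which C.2.9 gives effect sizes by sex. The severity is minor to moderate, and the remedy is a cheap improvement.

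**What to change.** - Reword the sentence in A.1 so that a non-significant Aim 1 result is not read as evidence of age-related change.
- In C.2.8, commit to reporting the sex difference in endotoxin effect (sex by condition) with its 95% CI. Call the result inconclusive when the interval includes gaps of the size seen in young adults.
- Rest any statement about change with age only on an explicit comparison with the cohort of 115 younger adults that carries the uncertainty of both estimates. The value 0.70 is itself an estimate and should not serve as a fixed threshold. Label the comparison exploratory, non-concurrent and low-powered, and state the differences in age and protocol length.

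The cost is a few sentences and, if a statement about age is wanted, one further analysis of the group's earlier study. Enrolment and procedures do not change. The downside is that a null result will often have to be reported as inconclusive.

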Methods: In a randomized, double-blind, placebo-controlled design, 115 participants (69 females, mean age 24.1 ± 6.3 years) received either low-dose endotoxin (0.8 ng/kg of body weight) or placebo (same volume of 0.9% saline). Blood sampling for IL-6 and TNF was obtained approximately every hour post-injection for the next six hours (T1-T6), along with assessment of social disconnection and depressed mood using the POMS. **Results:** Endotoxin (vs. placebo) led to significant increases in IL-6 ($P<0.001$) and TNF levels ($P<0.001$). Endotoxin (vs. placebo) also led to significantly greater increases in depressed mood ($P<0.001$), and these effects did not change when controlling for sickness symptoms ($P<0.05$) (Fig. 1). Additional analyses found that endotoxin induced increases in IL-6 and TNF which were similar between the two sexes, but suggested that women showed significantly greater increases in depressed mood than men in response to endotoxin ($P<0.05$). Similar results were found for feelings of social disconnection. **Conclusion:** Endotoxin induces increases in depressed mood, which are not due to sickness symptoms (i.e., headaches, muscle pain, shivering, nausea, breathing difficulties, and fatigue). Additional analyses suggested that women are more sensitive to an inflammatory challenge and show greater increases in depressed mood and social disconnection as compared to men. However, these analyses were limited to younger adults. Given the different hormonal milieu of younger vs. older women, and the regulation of inflammation by endocrine hormones, this study will evaluate inflammatory and affective responses in older adults stratified by sex and examine whether there are sex differences in inflammatory and affective responses.

C.1.1.2. Increases in inflammation correlate with depressive symptoms following endotoxin.

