Aim: To evaluate whether increases in inflammation account for increases in depressed mood following an inflammatory challenge. **Methods:** See C.1.3.1. **Results:** There were significant correlations between changes in IL-6 or TNF and social disconnection ($r = 0.27$, $P<0.05$; $r = 0.37$, $P<0.01$), and between changes in IL-6 or TNF and depressed mood ($r = 0.25$, $P<0.08$; $r = 0.30$, $P<0.05$). Additional analyses suggested that women showed more robust correlations than men. **Conclusion:** Levels of inflammation following endotoxin are associated with social affective responses, and these relationships appear to be stronger in younger women than men despite similar increases in inflammation in the two groups. This study will examine there are sex differences in affective sensitivity to inflammatory challenge in older adults.

[figure not shown]

Figure 1. Changes in depressed mood over 6 hours following endotoxin administration (vs. placebo)

C.1.1.3. Endotoxin safely induces increases in depressed mood in older females. *Aim*:

To evaluate the safety and feasibility of endotoxin administration in older females. *Methods*: In our ongoing study (K23AG049085, PI [name]), healthy older females aged 60-70 years (N=35) were entered into the previously described endotoxin protocol, which included hourly assessments of depressed mood using the POMS.

Results: None of the subjects had significant adverse events. Similar to prior results in younger adults, endotoxin was found to induce a significant increase in depressed mood ($P=0.017$; effect size 0.51), with peak increases in depressed mood at 2 hours; this timepoint of maximal increase is identical to our prior results (C.1.1.1). **Conclusion**: These data show that endotoxin can be safely administered to older females and induces increases in depressed mood with a similar time course of response.

C.1.2. Endotoxin-induced depressed mood predicts

subsequent depressive symptoms over 2 years. *Aim*:

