To examine whether transient increases in depressed mood during 6 hours following endotoxin administration predict subsequent depressive symptoms over a 2-year follow-up. *Methods*: In our ongoing study (K23AG049085, PI [name]), healthy older females aged 60-70 years who completed the above-described endotoxin protocol (N=22) were followed up for 21 months with an assessment of depressive symptoms every 3 months using the telephone-administered 9-item Patient Health Questionnaire (PHQ-9). **Results**: Endotoxin and placebo groups did not differ in subsequent depressive symptoms over 21 months ($P=0.37$), indicating that the intervention itself did not affect subsequent depressive symptoms (Fig. 2). In the endotoxin group, depressed mood assessed during 6 hours of experimental session at baseline strongly correlated with subsequent depressive symptoms over 21 months ($r = 0.71$, $P<0.0001$) (Fig. 3). However, in the placebo group, depressed mood assessed during 6 hours of experimental session did not correlate with subsequent depressive symptoms ($r = 0.07$, $P=0.74$). **Conclusion**: Transient increases in depressed mood following endotoxin administration strongly predict subsequent depressive symptoms over 2 years.

C.1.3. Increases in inflammation following influenza vaccine are associated with changes in reward processing. *Aim*:

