Figure 3. Correlations between endotoxin-induced depressed mood at baseline and subsequent depressive symptoms over 2 years (vs. placebo)

C.1.3. Summary of Preliminary Data

Inflammatory challenge induces depressed mood, especially in females; and increases in depressed mood correlate with increases in circulating markers of inflammation. Importantly, preliminary data suggest that older adults show similar increases in depressed mood in response to endotoxin as found in younger adult samples. Transient increases in depressed mood following endotoxin administration strongly predict subsequent depressive symptoms over 2 years. Prediction of clinical depression should be examined in a larger sample with appropriate diagnostic assessments in order to validate the endotoxin study procedures as a clinically relevant experimental model of depression.

C.2. RESEARCH DESIGN AND METHODS

C.2.1. Summary of the parent project

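### The older-women effect size of 0.51 behind Aim 1 does not reconcile with its own P=0.017 under a simple between-arm test, and the stated power above 80% is not delivered on any of the readings examined that would explain the pair

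*Combined protocol and SAP*

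**What the plan says.** The pilot is described in C.1.1.3: "healthy older females aged 60-70 years (N=35) were entered into the previously described endotoxin protocol", "which included hourly assessments of depressed mood using the POMS". The protocol it points back to, in C.1.1.1, was a parallel comparison: "In a randomized, double-blind, placebo-controlled design, 115 participants (69 females, mean age 24.1 ± 6.3 years) received either low-dose endotoxin". C.1.2 confirms that the older-women pilot also had two arms: "Endotoxin and placebo groups did not differ in subsequent depressive symptoms over 21 months". The C.1.1.3 result is that "endotoxin was found to induce a significant increase in depressed mood ($P=0.017$; effect size 0.51". No kind of effect size is named there.

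C.2.9 uses the same number for Aim 1 and states that "the effect size of endotoxin on depressed mood was still large but expectedly smaller ($d=0.51$) than in younger females". It combines this with 0.003, a value from younger men assumed to hold in older men, refers to matching and multivariate regression, and expects power above 80% at two-tailed alpha 0.05 with 40 older women and 40 older men.

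C.2.2 randomises these 80 people equally to endotoxin or placebo, stratified by sex, which makes 20 per sex-by-condition cell. C.2.8 names the sex and condition main effects and their interaction as the key results.

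**The concern.** A P value, a sample size and a standardised difference from a two-arm comparison determine one another. Here the three do not fit under the simplest test, so it is unclear what 0.51 measures.

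That matters because 0.51 is the only older-adult estimate in the Aim 1 sample size argument and the only figure set against 0.70 to suggest a weaker response in older than in younger women. If it is on a different scale from 0.70 and 0.003, the Aim 1 difference of 0.51 − 0.003 is not a difference between like quantities, and the power derived from it has no clear meaning.

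**Working it through.** **Inputs.** From C.1.1.3: N=35, P=0.017, effect size 0.51. From C.2.9: 0.70, 0.003, alpha 0.05 two-tailed. From C.2.2: 20 per cell. Arm splits, correlations and intraclass correlations (ICCs) below are assumptions; the documents give none.

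**1. Does 0.51 give P=0.017?** For two independent arms, t = d × √(n₁n₂/(n₁+n₂)) with df = 33.
- Split 18/17: t = 0.51 × √(306/35) = 1.51, two-sided P = 0.141 (one-sided 0.071).
- Split 25/10: t = 1.36, P = 0.18. Near-equal arms are the most favourable case.
- In reverse, P = 0.017 at 33 df needs t = 2.51, so d = 2.51/√(306/35) = 0.85 (0.94 at 25/10).

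**2. Readings that do not reconcile the pair.** Taking 0.51 as a correlation in 35 women gives P = 0.002. Taking it as Cohen's f (d = 1.02) gives P = 0.005.

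**3. Readings that do.**
- ANCOVA, with 0.51 on the raw SD and baseline correlation ρ: t = 1.508/√(1 − ρ²). At ρ = 0.80, t = 1.508/0.60 = 2.51 and P = 0.017.
- Change score, with 0.51 on the raw SD: t = 1.508/√(2(1 − ρ)). At ρ = 0.82, P = 0.017.
- Mean of six hourly scores, with 0.51 on the single-time SD: ICC of 0.2 to 0.3 gives P = 0.013 to 0.026.
- Within-arm effect in n women: t = 0.51 × √n. At n = 25, t = 2.55 and P = 0.0176. At n = 18, P = 0.045; at n = 35, P = 0.005.

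**4. The stated Aim 1 power.** The documents do not show how the figure above 80% was obtained.
- Treating the contrast 0.51 − 0.003 = 0.507 as 40 women against 40 men gives 61% unadjusted. It reaches about 80% with an assumed covariate correlation of 0.60, but that layout ignores the placebo half of each sex.
- For the sex-by-condition interaction at 20 per cell, SE = √(4/20) = 0.447 SD units, df = 76.

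| Input | Contrast / SE | Power |
|---|---|---|
| 0.51, unadjusted | 0.507/0.447 = 1.13 | 20% |
| 0.85, unadjusted | 0.847/0.447 = 1.89 | 46% |
| 0.51, ANCOVA at ρ = 0.80 | (0.507/0.60)/0.447 = 1.89 | 46% |

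- With 0.507, a correlation of 0.90 gives 73% and 0.92 gives 82%, so 80% needs a correlation above 0.9.
- Without adjustment, 80% needs about 123 per cell (492 in all) for 0.507, or 45 per cell (180 in all) for 0.847.

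**5. Precision.** At 18/17, the 95% CI for an unadjusted 0.51 is 0.51 ± 1.96 × √(35/306 + 0.51²/70), or −0.16 to 1.18. At the upper limit the interaction power is about 74% ((1.18 − 0.003)/0.447 = 2.63).

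The gap to younger women is 0.70 − 0.51 = 0.19. Assuming the 69 younger women in C.1.1.1 were split 34/35, its standard error is √(0.248² + 0.344²) = 0.424 and its 95% CI is −0.64 to 1.02.

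**The case against.** The strongest reply is that the two figures need not conflict. POMS was taken hourly, and C.2.8 plans mixed models for data of this kind, so a baseline-adjusted or repeated-measures test in the pilot is plausible. An effect can properly be tested against a smaller error SD and reported on the raw SD. That stands, and it is why the point is one of reconciliation.

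C.1.2 adds some support. It reports r=0.71 with P<0.0001 in the endotoxin arm, yet only 22 women were followed in both arms together. Even all 22 in one arm would give P of about 0.0002 from one row per person. The pilot's P values may therefore come from repeated rows.

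Three stronger inferences are tempting, and the documents do not support them.
- A reader might infer that 0.51 is wrong or impossible. The readings in step 3 show otherwise.
- A reader might infer that older women responded more than younger women, because 0.85 exceeds 0.70. That holds only if P came from an unadjusted test. Even then the difference is −0.15, with a 95% CI of about −1.00 to 0.70 under the same arm assumptions, so nothing is reversed.
- A reader might infer that C.2.9 contradicts the summary of preliminary data in C.1.3, which says "older adults show similar increases in depressed mood in response to endotoxin as found in younger adult samples". That comparison is with younger adult samples, and the one in C.1.1.1 is mixed-sex. Weighting by sex gives (69 × 0.70 + 46 × 0.003)/115 = 0.42, so 0.51 can be similar to that and still smaller than 0.70.

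It is also fair that Aim 2 is sized from other effect sizes (f² of 0.22 and 0.32) and its hypothesis argued from age trends in depression, so 0.51 does not carry Aim 2.

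**Conclusion.** The concern holds in a limited form. Under a simple between-arm test of 35 women, 0.51 and P=0.017 disagree: P would be 0.14, or d about 0.85. They can agree under other readings, but the documents do not say which applies. C.2.9 nevertheless treats 0.51 as a d on the same footing as 0.70 and 0.003.

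The practical consequence is for the Aim 1 power. It is about 20% with 0.51, and about 46% with 0.85 or with 0.51 under ANCOVA at an assumed correlation of 0.80. None of these reaches 80%. Keeping 0.51 would require a covariate correlation above 0.9, and C.2.9 states none. Taking 0.85 as a raw-SD effect would still require a further correlation of about 0.75 (0.847/√(1 − 0.75²) = 1.28; 1.28/0.447 = 2.86; power 81%).

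The statement that the older-women effect is "the effect size of endotoxin on depressed mood was still large but expectedly smaller" is unverified until the two values share a standardiser. Even at face value, the interval for the gap spans zero widely.

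These results assume near-equal pilot arms, unit SD in every cell, and 0.003 in older men as the plan does.

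**What to change.** From the pilot data in hand, compute one between-arm effect of endotoxin on POMS depression, with its 95% CI, on the scale of the planned Aim 1 analysis. State the test, arm sizes, standardiser and time window. Put that figure in both C.1.1.3 and C.2.9.

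Restate the Aim 1 sex-by-condition power in C.2.9 at 20 per cell from that estimate, over the range of its CI and with any assumed covariate correlation given, in place of the figure above 80%. Describe the older-women effect as smaller than the younger-women effect only if the recomputed value, on the same standardiser as 0.70, supports it.

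The cost is a short re-analysis and edits to two sections. The restated power will probably be less favourable. Nothing in this point calls for a change to trial conduct.
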